11.2. Study Candidate Screening

Investigators are responsible for screening all subjects and selecting those who are appropriate for study inclusion. The subjects selected for participation should be from the

^{*}Medication changes only will be captured

^{**}If additional procedure includes an additional ablation procedure in the LA with Rhythmia HDx mapping system, IntellaMap Orion mapping catheter and IntellaNav MiFi OI ablation catheter.

^{***} For details on Adverse Event and Device Deficiency reporting, please refer to Section 20.

PM007 Confidential

Form/Template 90702637 Rev/Ver AH LOCALIZE protocol, document 92142978, Rev/Ver AB Page 29 of 65

investigator's general patient population. The investigator is expected to follow standard of care testing to diagnose and screen subjects for inclusion in the study.

11.3. Informed Consent/Enrollment Visit

In order to determine eligibility of a subject, the investigator or designee needs to implement the consent process and verify/ document the subject meets the inclusion/exclusion criteria. Informed consent is required for all subjects (or their legal representatives) prior to their participation in the study. The subject should be given ample time to consider participation and ask questions if necessary. An approved informed consent form (ICF) shall be signed and personally dated by the subject (or legal representative). The original, signed document is to be kept with the subject's file and a copy must be provided to the subject. The index procedure must be performed within 60 days post ICF signature. In case the index procedure has not been performed within this time period, the subject will be classified as Intent (see section 10.3). The same subject cannot be considered for re-enrollment as re-enrollment is not allowed for any subjects in this study. The site will ensure that originally signed ICFs are filed in subjects' binders and that the ICF process is documented in the medical file. Originally signed ICFs and the ICF process will be made available for review at Interim Monitoring Visits (IMVs).

11.4. Baseline Visit

Subjects who provide consent and meet all of the study enrollment criteria will have baseline data collected.

The data collection at baseline includes:

- Visit date;
- Demographic data, including: age at time of consent, gender;
- Physical assessment including: height, weight, resting heart rate, systolic and diastolic blood pressure; medical history, including:
 - Underlying cardiovascular disease, including but not limited to hypertension, dyslipidaemia, cardiovascular artery disease;
 - Prior history of cardiac events including: acute myocardial infarction, ischemic stroke, hemorrhagic stroke or transient ischemic attack;
 - Prior surgical interventions and/or cardiac procedures (ablation excluded) including: Percutaneous Trans Catheter Angioplasty (PTCA), Coronary Artery Bypass Graft (CABG), pacemaker (PM) implantation, implantable cardioverter-defibrillator (ICD) implant, Cardiac Resynchronization Therapy (CRT) implant, cardiac valve interventions, left atrial appendage closure (LAAC), patent foramen ovale (PFO) intervention, heart transplant or procedures for implantation of other intracardiac devices;

- History of cardiac arrhythmias, including but not limited to time of first episode of PAF;
- Detailed history of all previous cardiac ablation procedures (catheter delivered or surgically performed), if any, including date of latest ablation procedure and any concomitant procedures (e.g., valve surgery, left atrial appendage closure or ligation, etc.), treated arrhythmia(s) and outcome;
- o Pre-procedure assessment of Left Ventricular Ejection Fraction, and left atrial diameter, if available;
- Non-cardiac comorbidities
- CHA2DS2-VASc score
- Current cardiovascular medication regimen including anti arrhythmic, anticoagulation andantiplatelet agents.

11.5. Index (ablation) procedure- Ablating physician BLINDED to DirectSense technology during initial encircling of PVIs (single blind masking)

The index ablation procedure (day 0) should be performed using standard of care methods established by the investigational center (e.g. sterile technique, personnel requirements, etc.). Study-related mapping and ablation with the Rhythmia HDx mapping system, the IntellaMap Orion mapping catheter and the IntellaNav MiFi OI ablation catheter should only be performed by physicians trained in Electrophysiology (EP) and authorized by BSC to perform study-related activities.

11.5.1. General information

The following general information on the procedure should be collected:

- Procedure date;
- Identification of study devices:
 - o Commercial Rhythmia HDx System; serial number
 - Commercially available Software Version 2.0 with DirectSense technology or any commercially available updates that are released during the course of the study;
 - o The IntellaMap Orion mapping catheter; catheter model, lot number
 - o The IntellaNav MiFi OI ablation catheter; catheter model, lot number
- Identification of non-study devices:
 - o Additional diagnostic catheters used during the case other than Orion including manufacturer, model and type
 - Sheaths used during the procedure including manufacturer, model and type

- Additional ablation catheter(s) used during the case other than IntellaNav MiFi OI including manufacturer, model, and type
- If concomitant procedures occurred during ablation procedure (e.g. ICD implant, PM, LAAC);
- LA access approach (trans septal, retrograde)
- Was heparin administered prior to or immediately following LA access according to guidelines?¹⁷
- Were ACT levels of 300 to 400 seconds achieved during the procedure according to guidelines?¹⁷
- The name of the EP physician performing the procedure

11.5.2. Procedural information

In order to avoid potential bias, the number of ablating physicians performing the index procedure and the month 3 assessment per investigational site is restricted to 2. Boston Scientific will therefore authorize maximum 2 ablating physicians per site.

Prior to starting the ablations, Rhythmia HDx + IntellaMap Orion will be used to collect an electroanatomic map (i.e. activation and voltage map) of the Left Atrium.

For all subjects it is preferred that all maps are acquired during pacing from the Coronary Sinus.

11.5.2.1. PVI ablation(s) - Ablating physician blinded to the DirectSense technology during initial encircling of PVs

It is recommended to limit the space between the center of 2 lesions to a maximum of 5 mm. The ablating physician is encouraged to avoid jumps between anatomical locations.

For the PVI ablation(s) the following information will be collected:

- Information related to PVI ablation(s):
 - o method of access to left atrium for ablation catheter, if applicable (transseptal, retrograde, or both);
 - type of PVI ablation application(s) (e.g. point (focal) lesions, dragging lesions*);
 - *The usage of dragging lesions for encircling the PVs will result in a Protocol Deviation. Dragging lesions or other types of applications are allowed for other arrhythmia(s)/additional lines.
 - specific PVI ablation technique(s) (WACA + information on additional lines if applicable)
 - o anatomical segments targeted for ablation (please refer to **Figure 11.5-2** for the 8 circumferential positions around each PV pair)
 - **Not targeting all anatomical segments for ablation will result in a Protocol Deviation.

PM007 Confidential

Form/Template 90702637 Rev/Ver AH LOCALIZE protocol, document 92142978, Rev/Ver AB Page 32 of 65

- Total number of RF applications per anatomical segment for PVI ablation;
- Power and duration for each RF application (cfr. printed EP Lab Procedure Report);
- Occurrence of steam pops;
- DirectSense data collection:
 - Blood pool impedance measurements for approximately 10 s prior to the 1st RF application (reference measurement)
 - Myocardium impedance measurements for approximately 10 s prior to the 1st RF application (reference measurement)
 - o Local impedance data will be sampled approximately every 50 ms. This data will be simultaneously recorded in a digital log file by the BSC representative.
 - Single ablation applications will be tagged by the Boston Scientific representative under guidance of the operating physician, in the Rhythmia HDx mapping system and on the Technical Source Form as:
 - belonging to a specific PV and anatomical segments.
 - resulting in steam pops.

Single applications in each anatomical segment will be tagged with ordinal numbers.

At the end of the PVI ablation(s), PVI will be confirmed by means of entrance block.

The waiting period before testing entrance block should be approximately 20 minutes. After this waiting period, Rhythmia HDx + IntellaMap Orion will be used to collect an electroanatomic map (i.e. activation and voltage map) of the Left Atrium. For all subjects it is preferred that all maps are acquired during pacing from the Coronary Sinus.

The following information will be collected in the eCRF:

• Number and location of gaps for each PV per segment, if any***

*** where feasible, the investigator should indicate approximate location respectively to the tagged ablation point

The BSC Rhythmia Mapping Specialist (RMS) supporting the procedure will be unblinded to the DirectSense technology during the entire procedure.

If the ablating physician becomes unblinded to the DirectSense technology during the initial encircling of the PVs, this will have to be documented on the Technical Source Form. For more details on the Technical Source Form, please refer to Section 13.4.

Form/Template 90702637 Rev/Ver AH LOCALIZE protocol, document 92142978, Rev/Ver AB Page 33 of 65

Gap closure, if applicable - Ablating physician UNBLINDED to the DirectSense technology

If gaps are identified and the ablating physician decides to ablate these gaps, the ablating physician will be unblinded to the DirectSense technology.

It is recommended to limit the space between the center of 2 lesions to a maximum of 5 mm. The ablating physician is encouraged to avoid jumps between anatomical locations.

For the gap closure, the following information will be collected:

additional point lesions

*The usage of dragging lesions for encircling the PVs will result in a Protocol Deviation. Dragging lesions or other types of applications are allowed for other arrhythmia(s)/additional lines.

• anatomical segments targeted for gap closure (please refer to **Figure 11.5-2** for the 8 circumferential positions around each PV)

**Not targeting all anatomical segments for ablation will result in a Protocol Deviation.

- Total number of RF applications per anatomical segment for gap closure;
- Power and duration for each RF application (cfr. Printed EP Lab Procedure Report);
- Occurrence of steam pops;
- DirectSense data collection:
 - o Local impedance data will be sampled approximately every 50 ms. This data will be simultaneously recorded in a digital log file by the BSC representative.
 - Single ablation applications will be tagged by the Boston Scientific representative, under guidance of the operating physician, in the Rhythmia HDx mapping system and on the Technical Source Form as
 - belonging to a specific PV and anatomical segments
 - resulting in steam pops.
 - Single applications in each anatomical segment will be tagged with ordinal numbers.
 - Local impedance data on the prior ablation line on both sides of the gap and on the gap itself must be recorded for approximately 10 s.

End of PVI

After touch ups of the gaps, Rhythmia HDx + IntellaMap Orion will be used to collect an electroanatomic map (i.e. activation and voltage map) of the Left Atrium. In case other arrhythmia(s)/additional lines will be ablated, these can be ablated prior to obtaining the electroanatomic map (i.e. activation and voltage map) of the Left Atrium. For all subjects it is preferred that all maps are acquired during pacing from the Coronary Sinus.

There is no requirement to implement a waiting period of approximately 20 minutes before obtaining this electroanatomic map. At the end of the PVI ablation(s), PVI will be confirmed by means of entrance block.

The following DirectSense data will be collected:

- Blood pool impedance measurements for approximately 10 s (reference measurement)
- Myocardium impedance measurements for approximately 10 s (reference measurement)
- Local impedance data will be sampled approximately every 50 ms. This data will be simultaneously recorded in a digital log file by the BSC representative.

The following information will be collected in the eCRF:

• Number of gap touch ups for each PV per each segment, if any***** where feasible, the investigator should indicate approximate location respect to the tagged ablation point

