7.1. Primary Endpoint

Primary endpoint is the association between baseline Local Impedance/Local Impedance drop values per anatomical segment as recorded at index ablation procedure and the proportion of gaps per anatomical segment as measured at the month 3 assessment. Local impedance data will be automatically recorded by the Rhythmia HDx mapping system during PVI for each ablation point. Impedance data will be analyzed offline to determine *Baseline Local Impedance* and *Impedance drops* for each ablation point. For the primary endpoint assessment, impedance data will be grouped per 8 anatomical segments around each PV pair (please refer to **Figure 11.5-2**). Distribution of ablation points and gaps during the index ablation procedure and at the month 3 assessment will be recorded during mapping and ablation with the Rhythmia HDx mapping system.

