12.1.1.2. Sample Size

A sample size of 60 subjects is chosen to generate 50 patients with usable data (20% attrition) and have 90% power to detect a minimum difference in DirectSense parameters of 3.71 ohms between segments with and without gaps at month 3.

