12.1.1.3. Statistical Methods

While no formal hypothesis test will be performed, 95% confidence intervals for the mean difference in baseline Local Impedance/Local Impedance drop values between segments with and without gaps will used to compare groups.

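### Each patient's pre-RF blood-pool impedance is recorded as a reference, but the stated baseline local impedance contrast does not use it and does not say how patient enters the interval

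*Combined protocol and SAP*

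**What the plan says.** Section 11.5.2.1 lists two pre-ablation values for each patient at the index procedure: "Blood pool impedance measurements for approximately 10 s prior to the 1st RF application (reference measurement") and "Myocardium impedance measurements for approximately 10 s prior to the 1st RF application (reference measurement"). The end-of-PVI list repeats both, for example "Blood pool impedance measurements for approximately 10 s (reference measurement"), and section 11.9 collects similar values at month 3.

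Section 7.1 describes how the primary variables are derived: "Impedance data will be analyzed offline to determine *Baseline Local Impedance* and *Impedance drops* for each ablation point". For the endpoint, "impedance data will be grouped per 8 anatomical segments around each PV pair". It gives no formula for the baseline value.

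Section 12.1.1.3 then compares groups by "95% confidence intervals for the mean difference in baseline Local Impedance/Local Impedance drop values between segments with and without gaps". It names no reference value, covariate, patient effect or clustering term. Sections 7.2 and 12.3.1 list further analyses, and none of them mentions the reference measurements either.

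**The concern.** Baseline local impedance is a level. Section 5.1.1 says that far-field effects influence it less than they influence generator impedance, which is not the same as no influence. Patients may therefore differ in level for reasons unrelated to the lesion. Each patient contributes up to 16 segments, and gaps need not be spread evenly over patients. An unadjusted gap versus no-gap difference then mixes a comparison within patients with a comparison between patients.

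Three things are at stake:

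- **Precision.** Patient offsets add noise to the difference.
- **Bias.** If patients with more gaps also tend to have a lower or higher impedance level, part of the difference is not a segment effect at all.
- **Meaning.** Section 6 wants usage guidance and a later lesion index. A threshold in ohms as displayed and a threshold allowing for the patient's blood pool are different guidance.

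The impedance drop is less exposed, because an additive offset cancels within one application. It is compared separately from baseline impedance, however. Two separate intervals cannot show whether the drop adds information beyond the baseline value of the same segment.

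**Working it through.** **1. The plan's own figure.** Section 12.1.1.2 claims "90% power to detect a minimum difference in DirectSense parameters of 3.71 ohms between segments with and without gaps at month 3", with 50 usable patients. No SD, gap rate or analysis unit is given, so the power cannot be reproduced, only solved backwards.

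- Implied standard error (SE), two-sided 5%: 3.71 / (1.960 + 1.282) = 1.144 ohm.
- Implied 95% half-width: 1.960 × 1.144 = 2.24 ohm.
- Implied SD for 50 × 16 = 800 independent segments, SD = SE / √(1/n₁ + 1/n₀): 7.1 ohm if 5% of segments have gaps (40 vs 760), 9.7 at 10% (80 vs 720), 13.0 at 20% (160 vs 640).

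Nothing here separates between-patient from within-patient variance, so everything below rests on assumed inputs.

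**2. Size of the offset effect, by formula.** Let τ be the between-patient SD, σ the within-patient SD and ICC = τ²/(τ² + σ²). If gaps fall evenly over patients and the reference explains a share R² of the offset variance, then SE(adjusted)/SE(unadjusted) = √(1 − ICC × R²). The upper limit, R² = 1, is:

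| ICC | Ratio | Half-width, from 2.24 ohm |
|---|---|---|
| 0.1 | 0.95 | 2.13 |
| 0.3 | 0.84 | 1.88 |
| 0.5 | 0.71 | 1.59 |
| 0.7 | 0.55 | 1.23 |

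An imperfect reference gains less. Take τ = 12, σ = 10, tissue-blood correlation r and reference error SD 1 ohm, so ICC = 144/244 = 0.59.

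- r = 0.9: R² = 0.81 × 144/145 = 0.804, ratio √(1 − 0.59 × 0.804) = 0.73.
- r = 0.3: R² = 0.09 × 144/145 = 0.089, ratio √(1 − 0.59 × 0.089) = 0.97.

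**3. With gaps clustered by patient.** Offsets then average out less in the gap group, so adjustment gains more. Simulations used 50 patients × 16 segments, σ = 10 ohm, gap rates of 5–10% and moderate gap clustering (patient SD about 1 on the logit scale).

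- **Covariate:** SE ratio 0.63 to 1.01 over r from 0 to 0.9. The gain is at most 4% for r of 0 to 0.3, and reaches 37% at r = 0.9 with offset SD 12 ohm.
- **Subtraction:** with equal SDs it leaves 2(1 − r) of the offset variance, which is 0.2 at r = 0.9, 0.6 at 0.7, 1.0 at 0.5 and 1.4 at 0.3. Simulated SE ratios were 0.80–0.93 at r = 0.7 and 0.99–1.03 at 0.5. At r of 0.3 or less they were 1.03–1.37.

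**4. Bias.** With a true difference of zero and an assumed correlation of −0.3 between blood offset and gap propensity, the unadjusted gap-minus-no-gap difference averaged about −0.5 to −2.9 ohm. At r = 0.9 and a 10% gap rate it was −1.0, −2.0 and −2.8 ohm for offset SDs of 4, 8 and 12. The largest of these is 2.8/3.71 = 75% of the target difference. The covariate contrast stayed within 0.3 ohm of zero.

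**5. Interval width.** With gaps clustered (assumed gap ICC 0.15) and clustering ignored, the nominal 95% interval covered about 92% of the time at impedance ICC 0.1, 85–89% at 0.3 and 80–82% at 0.5.

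**6. Overlap with a patient effect.** A random-intercept model weights between-patient information by σ²/(σ² + 16τ²). This is 100/356 = 0.28 at τ = 4, 100/1124 = 0.09 at τ = 8 and 100/2404 = 0.04 at τ = 12. Patient fixed effects remove that information altogether, and a single reference value per patient then cancels exactly.

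**The case against.** The strongest objection is that a patient effect is the more direct remedy. With patient fixed effects and no reference at all, the SE fell to about 0.89–0.93 of the unadjusted value at offset SD 4, 0.64–0.77 at SD 8 and 0.50–0.59 at SD 12. That is as good as or better than the reference alone. This stands: the gains quoted for the covariate are against an unadjusted difference and do not add to those of a patient effect. Step 6 shows that little between-patient information is left once a random effect is fitted. The covariate keeps its full effect if patient is handled by clustered errors around a pooled contrast. In either case it states on which impedance scale the result is read.

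Second, a reader might infer that the plan has chosen to analyse raw ohms pooled across patients. That is the plain reading of section 12.1.1.3, but it rests on silence. Section 7.1 gives no formula, and a blood-pool-subtracted value would also be in ohms, so the 3.71 ohm target does not settle it.

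Third, the documents neither quantify a patient offset nor say that blood pool tracks tissue. The myocardium value carries the same label. This also stands, and it is why subtraction should not be the primary method.

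Fourth, section 12.1.1.1 says no hypothesis is tested, section 12 describes itself as an overview, and the list of additional analyses is open. This lowers the urgency. It does not supply the missing definition of the primary comparison.

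**Conclusion.** The point holds as an omission with a better method at hand. The protocol records a pre-RF blood-pool reference for each patient, and no stated analysis uses it. The only stated contrast is unadjusted, and whether baseline local impedance is referenced is left open.

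Relative to that contrast, covariate adjustment changes the true SE by between about 0% and 37%, at almost no risk (worst simulated ratio 1.01). It also removes a bias of about 0.5 to 2.9 ohm in the scenario where blood offset and gap propensity correlate at −0.3. These figures depend on assumed offset SD, within-patient SD, tissue-blood correlation and gap clustering, none of which the documents give.

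Two stronger readings are not supported. One is that offsets simply widen the interval: if clustering is ignored, the interval can be too narrow for its true error. The other is that subtracting the blood pool reliably sharpens the result: that needs r well above 0.5, and the documents give no value of r.

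**What to change.** In section 12.1.1.3:

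1. Estimate the baseline local impedance contrast with the patient's pre-RF blood-pool reference as a covariate, in a model that accounts for patient by a random patient effect or patient-clustered errors. Name which in advance. Do not rely on patient fixed effects for this purpose, since the reference then cancels.
2. Report the unadjusted difference in ohms alongside. Use the blood-pool-subtracted value only as a supportive presentation.
3. As a supportive analysis, report the impedance drop contrast with and without the same segment's baseline local impedance in the model.

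In section 7.1, add the formula for baseline local impedance and say whether it is referenced.

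The cost is a few sentences of text and a small amount of analysis work. All values are already recorded, so there is no new measurement and no burden on patients. The choice should be fixed before the month 3 gap data are linked to the impedance data. Section 12.3.2 already provides for documenting a change of analysis in the study report.

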11.5.2.2. Ablation of other arrhythmia(s)/additional line(s)

In case other arrhythmia(s)/additional line(s) will be ablated, the PVI has to be achieved prior to ablating other arrhythmia(s)/additional line(s).

- If the other arrhythmia(s)/additional line(s) will be ablated in the LA, Rhythmia HDx + IntellaMap Orion will be used to collect an electroanatomic map (i.e. activation and voltage map) of the Left Atrium prior to ablating the other arrhythmia(s)/additional line(s) in the LA.
- If the other arrhythmia(s)/additional line(s) will not be ablated in the LA, the electroanatomic map (i.e. activation and voltage map) of the Left Atrium may be obtained after ablating the other arrhythmia(s)/additional line(s).

For the other arrhythmia(s)/additional line(s), the following information will be collected:

- O Type of ablation application(s) (e.g. point (focal) lesions, dragging lesions#); #Dragging lesions or other types of applications are allowed for other arrhythmia(s)/additional lines.
- Anatomical locations targeted for other arrhythmia(s)/additional line(s);
- Total number of RF applications per other arrhythmia(s)/additional location(s);
- o Technique used to ablate these other arrhythmia(s)/additional line(s);
- Successful termination of the arrhythmia(s), if applicable;
- o Power and duration for each RF application;
- Total RF application time for the other arrhythmia(s)/additional line(s);
- o Did steam pops occur;

11.5.2.3. Data collection after PVI ablation(s) and after ablation of other arrhythmia(s)/additional line(s), if applicable

At the end of the procedure the following information will be entered into the eCRF:

- Total Fluoroscopy time;
- Total procedure time will be collected, defined as time elapsed from time first access sheath insertion into the subject until the last catheter removed;
- Assessment of reportable Adverse Events/Device Deficiencies;
- Protocol Deviations, if applicable

At the end of the procedure, the following data must be saved/printed:

- The Rhythmia Advanced Export Case Data (the data collected through the Rhythmia HDx mapping system) will be saved and stored to external media, as provided by the sponsor.
- The EP Lab Procedure Report will be printed and stored in the center's patient file. Please refer to **Table 11.11-1** for an overview of source document requirements.

The Figure below describes the index procedure workflow.

Figure 11.5-1: Index Procedure Workflow

[figure not shown]
[figure not shown]

Figure 11.5-2: 8 Circumferential positions around each PV

